 - c. Unlikely to comply with the protocol requirements, instructions, and study-related restrictions (e.g., uncooperative attitude, inability to return for follow-up visits, and improbability of completing the study).
 - d. Have any medical or surgical condition, which in the opinion of the investigator would put the subject at increased risk from participating in the study.
 - e. Involved with, or a relative of, someone directly involved in the conduct of the study.
18. Any clinically significant disease or condition affecting a major organ system, including but not limited to gastrointestinal, renal, hepatic, endocrinologic, pulmonary, neurological, metabolic or cardiovascular disease.
19. Any surgical or medical condition which, in the judgment of the Investigator, might interfere with the pharmacokinetics, distribution, metabolism, or excretion of the study drug (if applicable).
20. Treatment with other investigational medicinal products or devices within 30 days or 5 half-lives, whichever is longer, prior to the administration of the study drug, planned use of investigational medicinal products or devices.
21. Previous participation in this study or any preceding study with ALN-PCS_{SC}.
22. Hypersensitivity to any of the ingredients of the study drug being used.

Test Drug, Dose and Mode of Administration, Batch Number(s):

The study drug (ALN-PCS_{SC}) will be administered by subcutaneous (SC) injection as a formulation of ALN-60212. It will be supplied as a sterile 100 mg vial (200 mg/mL solution) for SC injection. ALN-PCS_{SC} will be administered as a single SC injection of 300mg on Day 1. If mean serum PCSK9 levels are not suppressed by > 70% at Day 60 or 90, as compared to baseline, a second dose of 300mg will be administered at the next visit at Day 90 or 104 respectively.

Duration of Treatment: The expected duration of the subjects' involvement in the study will be approximately 208 days, which includes screening, study drug administration, and the follow-up period through EOS. However additional follow-up visits may occur every 30 days until Day 300 for subjects whose LDL-C reduction is less than 20% of the absolute reduction from baseline to Day 90 (for a maximum duration up to 328 days). If ALN-PCS_{SC} is found to be effective in lowering LDL-C in HoFH, a subsequent study may follow for subjects participating in the study.

Reference Therapy, Dose and Mode of Administration: There is no reference therapy in this study.

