Formation of anti-drug antibodies (ADA) will be assessed on Day 1 (prior to and 4 hours after the injection) and on subsequent visits until the end-of-study (EOS).

[figure not shown]
The EOS visit and the last estimation of lipids will occur at Day 180. Following Day 180 subjects will continue in the study until the observed LDL-C reduction is less than 20% of the absolute reduction from baseline to Day 90. Subjects will be encouraged to complete all planned visits.

The decision to initiate a Phase III study will be defined as an observed mean 15% or greater reduction in LDL-C. A number of factors may influence the proportion of subjects achieving this metric, in particular the specific LDL receptor mutation(s) or other causative mutations of HoFH

studied. Given the small sample size for this part of the study, such issues will be taken into careful consideration prior to making the final decision.

The efficacy and safety/ tolerability data from this study will be reviewed by a Safety Committee (SC) on an ongoing basis, and the results will be used to guide the decision to initiate a Phase III study. A recommendation may be taken to stop or amend the study at any of these reviews.

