- ^f Lab tests performed by study's designated Central Lab facility from enrollment to EOS. In addition, subjects in whom LDL-C reduction is less than 20% of the absolute reduction from baseline to Day 90 will continue to be followed up on a monthly visit schedule either until this level has been reached or until Day 300.
- ^g Urinalysis collection is prior to the injection on Day 1.
- ^h Urine pregnancy test performed at each visit for females of childbearing potential. In addition, postmenopausal women who are less than 55 years of age will have a pregnancy test within 24 hours of enrollment and prior to any study drug injection. Results must be available prior to the injection on Day 1 and, if a second dose of study drug is required, on Day 90/104.
- ⁱ Females of childbearing potential will have a pregnancy test at each additional follow-up visit until LDL-C reduction is less than 20% of the absolute reduction from baseline to Day 90.
- ^j Two ADA samples will be drawn on Day 1: one before the injection and one 4 hours after the injection.
- ^k Additional aliquots of plasma and serum will be collected at each time point and stored for future analyses.
- ^l For subjects in whom LDL-C reduction is less than 20% of the absolute reduction from baseline to Day 90, formation of ADA will be assessed at the last visit.
- ^m Efficacy parameters (Lipids / lipoproteins) will include LDL-C, total cholesterol, triglycerides, HDL-C, non-HDL-C, very low-density lipoprotein (VLDL-C), apolipoprotein A1 (Apo-A1), apolipoprotein B (Apo-B), lipoprotein(a) [Lp(a)], and PCSK9.
- ⁿ Day 270 only.
- ^o Sample may be taken during screening or anytime during study to be processed and stored, but only after separate consent has been signed.
- ^p Additional Follow-Up visits only for those subjects in whom LDL-C reduction is less than 20% of the absolute reduction from baseline to Day 90.
- ^q 3 aliquots of plasma and 3 aliquots of serum will be stored for efficacy and safety biomarker analysis if needed. All samples will be destroyed 1 year following the last subject's last visit in the study.

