6.7. Additional Follow-Up Visits (FU 8-11, if needed)

These visits are only for those subjects in whom LDL-C reduction is less than 20% of the absolute reduction from baseline to Day 90. Procedures will be as follows:

1. Blood samples drawn for clinical laboratory tests:
 - a. Biochemistry
 - b. Inflammatory markers
 - c. Lipids/lipoproteins
 - d. Hematology
 - e. Coagulation
 - f. HbA1c (only at Day 270)
 - g. Anti-ALN-PCSSC (ADA) antibodies (only at last visit)
 - h. Biomarkers (stored samples)
2. Urinalysis (local)
3. Urine pregnancy test (local). Females of childbearing potential will have a pregnancy test at each additional follow-up visit until LDL-C reduction is less than 20% of the absolute reduction from baseline to Day 90
4. Concomitant medications
5. AE reporting
6. SAE reporting

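### The rule for follow-up after Day 180 runs in opposite directions: Protocol 3.1 follows subjects until the LDL-C effect has faded, while the schedule and Protocol 6.7 admit only subjects in whom it already has

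*Protocol*

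**What the plan says.** The post-Day-180 rule is stated many times, in two directions. Each compares the current LDL-C reduction with 20% of the absolute reduction from baseline to Day 90.

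**Below 20% ends follow-up.** Protocol 3.1: "Following Day 180 subjects will continue in the study until the observed LDL-C reduction is less than 20% of the absolute reduction". The synopsis (Study Design), SAP 1.1 and SAP 5.2.3 say the same. Footnote i of the schedule agrees: "Females of childbearing potential will have a pregnancy test at each additional follow-up visit until LDL-C reduction is less than 20"%. Item 3 of Protocol 6.7 matches footnote i.

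**Below 20% is required to enter follow-up.** Footnote p in Protocol 6.1, repeated in SAP Table 1: "Additional Follow-Up visits only for those subjects in whom LDL-C reduction is less than 20% of the absolute reduction". Protocol 6.7: "These visits are only for those subjects in whom LDL-C reduction is less than 20% of the absolute reduction", and SAP 2.5 likewise. Protocol 10.3.3 defines the extended observation window the same way. The synopsis (Duration of Treatment) has this direction in softer form: "additional follow-up visits may occur every 30 days until Day 300 for subjects whose LDL-C reduction is less than 20% of the absolute reduction".

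**Both at once.** Footnote f, in both documents, takes subjects already below 20% and says they "will continue to be followed up on a monthly visit schedule either until this level has been reached or until Day 300".

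**ADA sampling.** Footnote l limits the final ADA sample to subjects with a reduction "less than 20% of the absolute reduction from baseline to Day 90, formation of ADA will be assessed at the last visit". Item 1g of Protocol 6.7 asks for ADA at the last additional visit without that condition.

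**The concern.** Sites work mainly from the schedule of assessments and the visit-procedure section. Those are the places that carry the reversed rule, and they carry it with the word 'only'. Followed literally, they send home at Day 180 the subjects who would show how long the effect lasts, and bring back those in whom there is little left to observe.

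Protocol 1.3 says the study was designed to test efficacy and duration of effect. That is a stated rationale and not a listed objective, but the secondary objectives do run to Day 180 or the final visit, so the data behind them depend on which rule is applied. Protocol 1.3 also reports a significant Phase I effect still present at 180 days. That was a different population and gives no rate for HoFH, but it makes persistence at Day 180 plausible. With 8-10 subjects at 2-5 centres in several countries, one site reading the rule differently would visibly change the late data.

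The analysis window is also affected. Both documents leave events outside the defined observational period out of the planned analysis and only list them. An event at Day 210 in a subject with a persisting effect falls outside the window in Protocol 10.3.3 and inside the one in SAP 5.2.3. SAP Section 7 nevertheless declares no changes from the protocol.

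**Working it through.** The plan gives no figure to reproduce. The check compares the wording and then counts visits.

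**Inputs**
- Additional visits FU8-FU11 at Days 210, 240, 270 and 300 (Protocol 6.1): 4 visits, 300 − 180 = 120 days.
- Sample size 8-10 (Protocol 4.1).
- Maximum participation 328 days (Protocol 6).

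**Direction.** Let r = (LDL-C reduction at Day 180) ÷ (absolute reduction from baseline to Day 90), with a positive Day 90 reduction.
- Protocol 3.1: continue if r ≥ 0.20.
- Footnote p, Protocol 6.7, SAP 2.5: additional visits only if r < 0.20.
- Footnote f, read literally: enter if r < 0.20 and stop once r < 0.20. Entry and stopping conditions coincide, so nobody is followed.

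The first two conditions are complements, so no subject satisfies both.

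**Illustration**, assuming a Day 90 reduction of 100 mg/dL, so a threshold of 0.20 × 100 = 20 mg/dL:
- Reduction of 60 mg/dL at Day 180 (r = 0.60): continues under 3.1; no additional visits under footnote p and 6.7.
- Reduction of 10 mg/dL at Day 180 (r = 0.10): finished under 3.1; eligible for FU8-FU11 under footnote p and 6.7.

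**Additional visits per subject under each reading**

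| Reduction first below 20% at | Protocol 3.1 | Footnote p / 6.7 | Footnote f, literal |
|---|---|---|---|
| Day 180 | 0 | up to 4 | 0 |
| Day 210 | 1 | 0 | 0 |
| Day 240 | 2 | 0 | 0 |
| Day 270 | 3 | 0 | 0 |
| Day 300 or never | 4 | 0 | 0 |

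The footnote p / 6.7 column assumes the 20% test is applied once, at Day 180. Those texts do not say when it is applied, but a subject discharged at Day 180 has no later scheduled lipid sample on which to apply it.

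**Bounds across the trial.** Visits lost by following footnote p and 6.7 instead of 3.1:
- Lower bound 0, if every subject is below 20% at Day 180.
- Upper bound 4 × 8 = 32 to 4 × 10 = 40, if every subject stays at 20% or more through Day 270.

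**Do the stated durations settle the direction?** No. 28 + 180 = 208 and 28 + 300 = 328 days match the synopsis under either reading.

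**ADA.** Under the 3.1 rule, a subject still at 20% or more at Day 300 is outside footnote l but inside item 1g of 6.7.

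**The case against.** The strongest reply is that the intent is plain and this is a drafting slip. Footnote i, item 3 of 6.7 and SAP 5.2.3 all run in the 3.1 direction, and the end of footnote f makes sense only as a stopping rule. On that view a site would go wrong only by applying the first sentence of 6.7 and ignoring both item 3 of that section and Section 3.1. This is right about intent and supports choosing the 3.1 direction, but the restrictive sentences remain in force where sites look.

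Other points limit the weight:
- The 32-40 figure is an extreme. It needs every effect to persist and every site to take the reversed reading. It is a bound and not an expectation.
- Zero visits under footnote f shows that the sentence is incoherent; no site is likely to act on it that way.
- The ADA gap is small, because item 1g already covers everyone attending. Lipids at FU8-FU11 are likewise already scheduled, despite the text in 3.1 placing the last lipid measurement at Day 180.
- The safety loss is partial. ADA is sampled at Day 180, ongoing SAEs are followed to resolution (6.6), existing AEs until they resolve or stabilise (8.1.1), and post-study SAEs and AESIs may be reported (8.3.2). Protocol 8.3.1 also stops non-serious AE recording at EOS although the schedule marks it at the additional visits, so loss of late AE data is not wholly due to this rule.
- Neither wording handles a zero or negative Day 90 reduction. If LDL-C were 50 mg/dL above baseline at Day 90, the threshold would be −10 mg/dL, and a subject back at baseline on Day 180 would count as retaining effect. That gap is in the existing rule too.
- The design schematics are not shown, and the Netherlands-specific Amendment 2.0 cited in the SAP was not available. It may have corrected the text for Dutch sites, but the SAP that cites it still carries both directions.

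**Conclusion.** The concern holds. Current text in both documents makes the same 20% threshold a stopping rule in some places and the entry rule in others, and nothing in the available documents says which governs. A persistent subject loses 1 to 4 visits, at most 120 days of follow-up; the trial total lies between 0 and 32-40 visits and cannot be narrowed from the documents. These counts assume a positive Day 90 reduction and a single eligibility assessment at Day 180.

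The primary endpoint at Days 90 and 180, the responder rate and the 15% criterion do not depend on the rule. What is at risk is the late evidence on duration of effect, part of the late ADA and safety data, and a consistent observation window. This should be fixed; it does not threaten the primary result.

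**What to change.** Use the Protocol 3.1 direction everywhere, with wording such as:

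> Additional follow-up visits are for subjects whose LDL-C reduction at Day 180 is still 20% or more of the absolute reduction from baseline to Day 90, continuing monthly until it is less than 20% or until Day 300.

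Places to change:
- the synopsis text on duration of treatment;
- footnotes f, l and p in Protocol 6.1 and SAP Table 1;
- the first sentence of Protocol 6.7 and of SAP 2.5;
- Protocol 10.3.3, to match SAP 5.2.3.

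Footnote l should require ADA at the last additional visit for every subject in additional follow-up, including those still at 20% or more at Day 300. Footnote i and item 3 of 6.7 can stay. As minor tidying, the statement in the synopsis, Protocol 3.1 and SAP 1.1 that the last lipid measurement is at Day 180 should allow for lipids at FU8-FU11. It would be sensible to add how a zero or negative Day 90 reduction is handled. A note in SAP Section 7 is optional.

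The cost is wording in the SAP and a protocol amendment, with the usual IRB/EC approval. No visits or tests are added beyond those already scheduled, and the 328-day maximum stands.

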3.2. Schematic Diagram of Trial Design

3.3. Primary Endpoint

The primary endpoint of this trial is percentage change in LDL-C.

3.4. Secondary Endpoint(s)

The secondary endpoints of this trial are:

- Absolute change and percentage change in LDL-C
- Absolute change and percentage change in PCSK9 levels
- Absolute change and percentage change in total cholesterol, triglycerides, HDL-C, non-HDL-C, VLDL-C, Apo-A1, Apo-B, and Lp(a)

3.5. Exploratory Endpoint(s)

The exploratory endpoints of this trial are:

- Anti-drug antibodies (ADA) to ALN-PCS_{SC}
- Response of LDL-C reduction by underlying causal mutations of HoFH

3.6. Measures to Minimize/Avoid Bias

This is an unblinded, open label study. The primary endpoint is based on an assessment of LDL-C, which is a measurement that is not likely to be subject to interpretation bias.

3.7. Safety Committee (SC)

A Safety Committee (SC) will review efficacy and safety data and serious adverse events on an ongoing basis, and the results will be used to guide the decision to initiate a Phase III study. A recommendation may be taken to stop or amend the study at any of these reviews.

4. SUBJECT POPULATION

4.1. Number of Subjects

In this study, 8-10 subjects will be enrolled at 2-5 multi-national centers.

4.2. Inclusion Criteria

Subjects may be included in the study if they meet all of the following criteria:

1. Males and females, ≥ 12 years of age with a diagnosis of homozygous familial hypercholesterolemia by genetic confirmation or a clinical diagnosis based on a history of an untreated LDL-C concentration >500 mg/dl (13 mmol/L) together with either xanthoma before 10 years of age or evidence of heterozygous familial hypercholesterolemia in both parents.
2. Stable on a low-fat diet.
3. Stable on their pre-existing, lipid-lowering therapies (such as statins, cholesterol-absorption inhibitors, bile-acid sequestrants, or combinations thereof) for at least 4 weeks with no planned medication or dose change for the duration of study participation.
4. Fasting central lab LDL-C concentration >130 mg/dl (3.4 mmol/L) and triglyceride concentration < 400 mg/dL (4.5 mmol/L).
5. Bodyweight of 40 kg or greater at screening.
6. Subjects should be willing and able to give written informed consent before initiation of any study-related procedures (if the subject is less than 18 years of age, written consent will be obtained from their guardian or legally authorized representative, with verbal assent from the child). The subject should be willing to comply with all required study procedures.

4.3. Exclusion Criteria

Subjects will be excluded from the study if any of the following exclusion criteria apply prior to enrollment:

1. LDL or plasma apheresis within 8 weeks prior to the screening visit, and no plan to receive it during the study because of the attendant difficulty in maintaining stable concentrations of LDL-C while receiving apheresis.
2. Use of Mipomersen or Lomitapide therapy within 5 months of screening.
3. Previous treatment with monoclonal antibodies directed towards PCSK9 within 8 weeks of screening.
4. New York Heart Association (NYHA) class III or IV heart failure or last known left ventricular ejection fraction $< 30\%$ or any cardiac arrhythmia within past 3 months that is not controlled by medication.
5. Myocardial infarction, unstable angina, percutaneous coronary intervention (PCI), coronary artery bypass graft (CABG) or stroke within 3 months of enrollment.

6. Planned cardiac surgery or revascularization.
7. Uncontrolled severe hypertension: systolic blood pressure >180 mmHg or diastolic blood pressure >110 mmHg prior to enrollment despite anti-hypertensive therapy.
8. Poorly controlled diabetes mellitus, i.e., glycated hemoglobin A1c (HbA1c) >10.0% prior to enrollment.
9. Estimated glomerular filtration rate (eGFR) < 30 ml/min/1.73m².
10. Active liver disease defined as any known current infectious, neoplastic, or metabolic pathology of the liver or unexplained alanine aminotransferase (ALT), aspartate aminotransferase (AST), elevation > 3x the upper limit of normal (ULN), at screening confirmed by a repeat measurement at least 1 week apart.
11. Creatine kinase (CK) > 5x ULN without a known cause.
12. Other serious comorbid disease in which the life expectancy of the subject is shorter than the duration of the trial (e.g., acute systemic infection, or other serious illnesses).
13. Any history of malignant disease, with the exception of treated basal-cell carcinoma occurring >5 years before screening.
14. Females who are pregnant or nursing, or who are of childbearing potential (includes adolescent females who have reached menarche and are sexually active) and unwilling to use at least two methods of contraception (e.g., oral contraceptives, barrier methods, approved contraceptive implant, long- term injectable contraception, intrauterine device) for the entire duration of the study. Exemptions from this criterion:
 - a. Women >2 years postmenopausal (defined as 1 year or longer since their last menstrual period) AND more than 55 years of age
 - b. Postmenopausal women (as defined above) and less than 55 years old with a negative pregnancy test within 24 hours of enrollment
 - c. Women who are surgically sterilized at least 3 months prior to enrollment
 - d. Adolescent females who have not reached menarche
15. Males who are unwilling to use an acceptable method of birth control during the entire study period (e.g., condom with spermicide).
16. Known history of alcohol and/or drug abuse within 5 years.
17. Any condition that according to the investigator could interfere with the conduct of the study, such as but not limited to:
 - a. Inappropriate for this study, including subjects who are unable to communicate or to cooperate with the investigator.
 - b. Unable to understand the protocol requirements, instructions and study-related restrictions, the nature, scope, and possible consequences of the study (including subjects whose cooperation is doubtful due to drug abuse or alcohol dependency).
 - c. Unlikely to comply with the protocol requirements, instructions, and study-related restrictions (e.g., uncooperative attitude, inability to return for follow-up visits, and improbability of completing the study).

- d. Have any medical or surgical condition, which in the opinion of the investigator would put the subject at increased risk from participating in the study.
 - e. Involved with, or a relative of, someone directly involved in the conduct of the study.
18. Any clinically significant disease or condition affecting a major organ system, including but not limited to gastrointestinal, renal, hepatic, endocrinologic, pulmonary, neurological, metabolic or cardiovascular disease.
 19. Any surgical or medical condition which, in the judgment of the Investigator, might interfere with the pharmacokinetics, distribution, metabolism, or excretion of the study drug (if applicable).
 20. Treatment with other investigational medicinal products or devices within 30 days or 5 half-lives, whichever is longer, prior to the administration of the study drug/device, planned use of investigational medicinal products or devices.
 21. Previous participation in this study or any preceding study with ALN-PCS_{SC}.
 22. Hypersensitivity to any of the ingredients of the study drug being used.

Subjects excluded for any of the above reasons may not be re-screened for participation at any time if the exclusion characteristic has changed.

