5.2.2. Prohibited Concomitant Medications

The following medications/treatments are not permitted to be added during the study:

- Medications used to lower LDL-C (eg, statins, ezetimibe, lomitapide, mipomersen, niacin, colesvelam, bile acid absorption inhibitors, monoclonal antibodies directed towards PCSK9).

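### Exclusion 1 (apheresis) has its polarity reversed: on either literal reading, a plan for on-study apheresis is not itself a ground for exclusion, contrary to the criterion's own stated reason

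*Protocol*

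**What the plan says.** The lead-in to Protocol Section 4.3 sets how every item works: "Subjects will be excluded from the study if any of the following exclusion criteria apply prior to enrollment". An item that is true of a subject therefore removes that subject.

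Item 1 is "LDL or plasma apheresis within 8 weeks prior to the screening visit, and no plan to receive it during the study". The sentence goes on to give its reason: "because of the attendant difficulty in maintaining stable concentrations of LDL-C while receiving apheresis". The Synopsis carries the same item in the same words, so it does not correct Section 4.3.

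Two other items in the list deal with planned events, and both state the plan itself as the ground for exclusion: item 6, "Planned cardiac surgery or revascularization", and item 20, "planned use of investigational medicinal products or devices".

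The SAP has no eligibility criteria of its own. Its Section 5.3.3 lists subjects with protocol deviations, and Protocol Section 12.3 names violations of inclusion and exclusion criteria among the deviations to be documented.

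**The concern.** Having no plan for apheresis is something one would require of a subject entering this study. Placed in a list that excludes when an item applies, it works backwards.

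The primary endpoint is percent change in LDL-C at Days 90 and 180, in one arm without a control, in 8-10 subjects. Apheresis during the study would act on that measurement directly, and the criterion says as much. If the wording does not bar a subject who plans apheresis, that subject can enter without breaching item 1. No exclusion violation then arises under Section 12.3, and the SAP 5.3.3 listing need not show the subject on that account. A reader of the mean, which informs the 15% criterion for going on to Phase III (Protocol Section 3.1), would lose one of the ordinary warnings.

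**Working it through.** The plan states no figure on this point, so the check is one of logic.

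**Step 1. Inputs.** Let R be apheresis in the 8 weeks before screening, and P a plan to receive it during the study. Both come from item 1. The lead-in fixes the operation: item true means excluded.

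**Step 2. Candidate rules.**
- Reading A, one joint condition: exclude if R and not P.
- Reading B, the comma and *and* separating two grounds: exclude if R or not P.
- Rule implied by the stated reason: exclude if R or P.

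**Step 3. The four kinds of subject.**

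| Recent (R) | Planned (P) | Reading A | Reading B | Implied by the reason |
|---|---|---|---|---|
| yes | no | excluded | excluded | excluded |
| yes | yes | not excluded | excluded | excluded |
| no | yes | not excluded | not excluded | excluded |
| no | no | not excluded | excluded | not excluded |

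Reading A excludes 1 of 4 kinds and Reading B excludes 3 of 4. Each matches the implied rule in 2 of 4. The row that both get wrong is *not recent, planned*. The *recent, planned* subject is excluded under B, but by the recent-apheresis limb and not by the plan. B also excludes the *neither* subject, so the only people it admits are those who plan apheresis.

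**Step 4. Does anything else bar that subject?**
- Inclusion 3 requires stable lipid-lowering therapies "with no planned medication or dose change for the duration of study participation". Its examples are all drugs, and this clause is limited to medication.
- Exclusion 17 covers "Any condition that according to the investigator could interfere with the conduct of the study". It could be used, but it rests on the individual investigator's judgement.
- Section 5.2.2 begins "The following medications/treatments are not permitted to be added during the study". Its single bullet lists LDL-C-lowering medications.
- Section 5.4 (subject restrictions) covers fasting, blood donation and exercise.

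None of these names apheresis. In the available text the word occurs only in item 1, in its two places.

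**Step 5. Size, as illustration only.** Let apheresis lower a subject's Day 1 LDL-C by fraction a and the Day 90 or 180 value by fraction b, and let d be the true fractional fall on drug. One such subject among n moves the mean percent change by

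100 × (1 − d) × [(1 − b)/(1 − a) − 1] / n.

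The documents give n = 8 to 10. The range of 20% to 60% for a and b is my assumption. With d = 0:
- a = 0, b = 0.2 to 0.6: −20/8 to −60/8 = −2.5 to −7.5 points (n = 8); −2 to −6 (n = 10).
- a = b: 0.
- a = 0.6, b = 0.2: 0.8/0.4 − 1 = +1, so +12.5 points (n = 8) or +10 (n = 10).

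For a subject with no recent apheresis, a exceeds 0 only if a session falls between screening and Day 1. Under Reading A, subjects with recent apheresis who plan more also enter, and their Day 1 value may be lowered. The sign therefore depends on timing that the documents do not give.

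**The case against.** The strongest reply is that nobody will misapply this. The reason stands in the same sentence, and both literal readings give absurd results: A bars recent users only if they have stopped, and B admits only those who plan apheresis. Item 20 is itself a loosely joined fragment, so the list's drafting pattern is weak evidence. All of this stands. It is why the severity is modest, and it does not make the operative wording correct. The study runs at 2-5 multinational centers, and violations are judged against the text.

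Three stronger readings are tempting, and the documents do not support them.

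- *The protocol excludes only recent users without a plan and lets in everyone who plans apheresis.* That is Reading A alone. Under Reading B a subject with recent and planned apheresis is excluded. Only the conclusion common to both readings should be relied on.
- *The error biases the mean towards the drug and could carry it past 15%.* No such subject is shown to have been enrolled, the size is assumed, and the shift can be negative, zero or positive. The primary analysis is descriptive, and Section 3.1 leaves the Phase III decision to judgement.
- *Apheresis would go unrecorded.* The visit schedule has no row for it, but the schedule is not the eCRF, which is not available. Section 7.1.2 collects ongoing medical and surgical issues and SAP 5.3.2 summarizes medical history, so it might be visible there.

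**Conclusion.** The concern holds in this form: on both literal readings of item 1, a plan for on-study apheresis is not a ground for exclusion, and a subject with planned but no recent apheresis is not excluded. This contradicts the criterion's own reason. Inclusion 3 and exclusion 17 are partial backstops only. Such a subject could enter without an exclusion violation being recorded under Section 12.3 and listed under SAP 5.3.3.

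This is a drafting (polarity) error in operative text. A reader might infer a deliberate choice to allow apheresis, but the stated reason points the other way. Severity is modest because the intent is recoverable. No numerical effect on the mean is established. The finding on the wording is firm for the 07 November 2016 protocol. The Netherlands-specific Amendment 2.0, cited in SAP Section 8, was not available to check.

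**What to change.** Reconcile item 1 with its stated reason in both the Synopsis and Section 4.3. Word recent apheresis and planned on-study apheresis as two separate conditions, each with the polarity the sponsor intends, in the way items 6 and 20 treat planned events. Which subjects are eligible is for the sponsor to state. Check that Amendment 2.0 does not carry the same wording.

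The cost is a few words in two places, made through an amendment that needs IRB/EC approval (Section 13.2). No change to the SAP analyses is needed. Once the criterion reads correctly, a breach counts as an exclusion violation under Section 12.3 and reaches the existing SAP 5.3.3 listing.
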